18.2 Institutional Review Board (IRB) and Informed Consent

The IRB-approved consent form must include all elements required by FDA, state, and local regulations, and may include appropriate additional elements. Before study initiation, the Investigator must have written and dated approval from the IRB for the protocol, consent form, subject recruitment materials/process (e.g., advertisements), and any other written information to be provided to subjects or LARs. The Investigator should also provide the IRB with a copy of the product labeling, information to be provided to subjects or LARs and any updates. The Investigator will submit documentation of the IRB approval to the Sponsor. Copies of all correspondence with the IRB regarding this study must be sent to the Sponsor.

The Investigator or designee will explain the study to each potential subject and LAR and the subject or LAR must indicate voluntary consent by signing and dating the approved informed consent form. The Investigator or designee must provide the subject or LAR with a copy of the consent form in a language the subject or LAR understands. The Investigator will maintain documentation that informed consent was obtained prior to the initiation of any study-specific procedures. Any failure to obtain informed consent must be reported to the IRB and Sponsor.

Withdrawal of IRB approval must be reported to the Sponsor within 5 working days.

18.3 Protocol Compliance and Protocol Deviations

The Investigator and all designees will comply with the IRB-approved protocol. All deviations from the protocol must be documented. The Investigator or designee will notify the Sponsor immediately if a deviation from the protocol was required to protect patient safety.

Any reproduction in part or whole without the written permission of Enspectra Health, Inc. is prohibited.

A large black rectangular redaction box covers the majority of the page content, starting below the header and ending above the footer. The redaction is irregular at the bottom, showing some white space and a small white rectangular area on the right side.

Appendix A: Sample Representation Across Patient and Lesion Characteristics

1. Purpose

To determine the chance of observing sufficient variability in subject and lesion characteristics that may impact reviewer ability to assess images. Specifically, the goal was to determine whether the planned sample sizes of 20 for the training set and 30 for the validation set were sufficient to observe representation of subgroups for underlying skin condition, Fitzpatrick skin type, lesion location, age group and sex with high probability.

2. Methods

Each characteristic was modeled separately. Frequency distribution estimates were obtained from recent literature. A simulation analysis was performed using SAS version 9.4. The simulation algorithm was as follows:

1. Simulate the appropriate number of subjects (20 for the training set or 30 for the validation set).
2. Assign subgroup categories using a multinomial distribution.
3. Count the number of subjects in each subgroup.

This process was repeated 10,000 times for each subject or lesion characteristic, and the count distribution over each subgroup level was examined. The minimum expected number was defined as the 10th percentile, that is, out of 10,000 trials the chance of observing at least that many was 90%. The average count (empirical expected value) was also recorded.

3. Results

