*Sample ranges based on 10th (lower) and 90th (upper) percentiles from simulations (see Appendix A). Minimum value for the number of samples required in the study is the lower bound of the range (derived from 10th percentile). There is no maximum value for any sample type.

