13.1 Sample Size Determination

The sample sizes of 20 subjects for the training set and 30 subjects for the validation set were determined by simulation studies (see Appendix A). The goal of these studies was to select sample sizes with a high probability of representation in as many of the subgroups of interest as possible. These sample sizes provide a $> 90\%$ chance of representation for underlying conditions of interest and Fitzpatrick skin type groups. In addition, these sample sizes reliably provide variability across age groups, genders and lesion locations.

If areas are assumed to be independent, the sample size of at least 360 areas in the validation set will produce confidence intervals with a width of $\pm 6.2\%$. The areas are correlated, which decreases precision, but the number of areas is expected to be larger, which increases it. If these factors offset, a confidence interval width of $\pm 6.2\%$ is a reasonable estimate of the expected results.

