3.1. Underlying skin condition

There is a 90% chance (10th percentile) of seeing at least 1 SCC and 2 BCC lesions in the training set. There is a 75% chance (25th percentile) of seeing at least 2 SCC and 3 BCC lesions in the training set (Table 3.1.2).

There is a 90% chance (10th percentile) of seeing at least 2 SCC and 4 BCC lesions in the validation set. There is a 75% chance (25th percentile) of seeing at least 4 SCC and 5 BCC lesions in the validation set (Table 3.1.3).

Table 3.1.1. Underlying data by underlying skin condition.⁴

Group	% of Skin Biopsy-Receiving Population
Basal cell carcinoma (BCC)	21.2%
Squamous cell carcinoma (SCC)	16.7%
Other	62.2%

Table 3.1.2. Simulations for training set (N=20) by underlying skin condition.

Group	N sims	10 th Pctl	EV	Std Dev	Min	1 st Pctl	25 th Pctl	Median	75 th Pctl	90 th Pctl	99 th Pctl	Max
BCC	10,000	2	4.3	1.84	0	1	3	4	5	7	9	12
SCC	10,000	1	3.3	1.68	0	0	2	3	4	6	8	12
Other	10,000	10	12.4	2.17	4	7	11	12	14	15	17	20

Table 3.1.3. Simulations for validation set (N=30) by underlying skin condition.

Group	N sims	10 th Pctl	EV	Std Dev	Min	1 st Pctl	25 th Pctl	Median	75 th Pctl	90 th Pctl	99 th Pctl	Max
BCC	10,000	4	6.4	2.25	0	2	5	6	8	9	12	16
SCC	10,000	2	5.0	2.05	0	1	4	5	6	8	10	13
Other	10,000	15	18.6	2.69	9	12	17	19	20	22	25	27

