3.5. Sex

The chance that both sexes are represented in the training set is close to 100%. The chance of obtaining samples for at least 7 patients for each sex is 90% (Table 3.5.2).

The chance that both sexes are represented in the validation set is close to 100%. The chance of obtaining samples for at least 11 patients for each sex is 90% (3.5.3).

Table 3.5.1. Underlying data by sex.²⁴

Group	% of positive NMSC diagnosis population
Female	50%
Male	50%

Table 3.5.2. Simulations for training set (N=20) by sex.

Group	N sims	10 th Pctl	EV	Std Dev	Min	1 st Pctl	25 th Pctl	Median	75 th Pctl	90 th Pctl	99 th Pctl	Max
Female	10,000	7	10.0	2.23	2	5	9	10	12	13	15	18
Male	10,000	7	10.0	2.23	2	5	8	10	11	13	15	18

Table 3.5.3. Simulations for Validation Set (N=30) by sex.

Group	N sims	10 th Pctl	EV	Std Dev	Min	1 st Pctl	25 th Pctl	Median	75 th Pctl	90 th Pctl	99 th Pctl	Max
Female	10,000	11	15.0	2.74	5	9	13	15	17	19	21	25
Male	10,000	11	15.0	2.74	5	9	13	15	17	19	21	25

Any reproduction in part or whole without the written permission of Enspectra Health, Inc. is prohibited.

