1.1.1.2 Minimize bias in assignment, and

1.1.1.3 Meet minimum enrollment targets for both the Training and Validation sets as specified in the study protocol.

1.1.2 To assign samples, 500 randomization assignment schedules will be generated. The first schedule that simultaneously meets the minimum enrollment targets for both the Training set and Validation set, and meets the requirement of a maximum Standard Mean Difference (SMD) <0.2 will be selected and used to assign samples to these sets.

¹ Austin PC. Balance diagnostics for comparing the distribution of baseline covariates between treatment groups in propensity-score matched samples. *Stat Med*. 2009;28(25):3083-3107. doi:10.1002/sim.3697

² Cohen J. *Statistical Power Analysis for the Behavioral Sciences* (2nd edn). Lawrence Erlbaum Associates Publishers: Hillsdale, NJ, 1988.

meeting pre-specified requirements. This schedule will be used to assign

The study protocol requires a minimum enrollment of (50) subjects, and assignment of 20 subjects to the Training Set and 30 subjects to the Validation Set. If more than 50 subjects are enrolled, excess subjects will be assigned to maintain the original ratio (40% of subjects assigned to the Training Set, 60% of subjects assigned to the Validation Set).

1.2.10 Validation of the Assignment Spreadsheet.

1.2.10.1 Prior to usage with real study data, the Assignment Spreadsheet will be tested and validated with simulated data. To generate a simulated data set, randomized categories will be assigned to hypothetical subjects using the probabilities expected in the population (Tables 1-5).

[REDACTED]

[REDACTED]

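### Appendix A gives the chance of meeting each subgroup minimum alone, but the plan requires all minima together; five paired probabilities and the training-set part of the >90% in 13.1 are too high.

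*Combined protocol and SAP*

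**What the plan says.** Appendix A, Methods, states that "Each characteristic was modeled separately". It takes the minimum for each subgroup level as the 10th percentile of that level's simulated count, explaining that "out of 10,000 trials the chance of observing at least that many was 90"%.

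The Results then attach these percentiles to pairs of levels. In 3.1: "There is a 90% chance (10th percentile) of seeing at least 2 SCC and 4 BCC lesions in the validation set", and "There is a 75% chance (25th percentile) of seeing at least 4 SCC and 5 BCC lesions in the validation set". In 3.5, for training: "The chance of obtaining samples for at least 7 patients for each sex is 90"%. Section 3.2 does the same for Fitzpatrick Type I with Types IV-VI.

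The footnote to Tables 1-5 in section 11.2 makes the percentiles binding: "Minimum value for the number of samples required in the study is the lower bound of the range". Appendix C 1.1.2 generates 500 assignment schedules and uses "The first schedule that simultaneously meets the minimum enrollment targets for both the Training set and Validation set", provided the maximum SMD is also below 0.2.

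Section 13.1 rests the sizes of 20 and 30 on representation and claims more than a 90% "chance of representation for underlying conditions of interest and Fitzpatrick skin type groups". Section 10.1 allows up to 15 further subjects, for a maximum of 65, to achieve the intended distribution.

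**The concern.** A 90% chance for each of several requirements is not a 90% chance of meeting them all. There are 12 non-zero minima in the training set and 13 in the validation set, and the assignment procedure needs every one of them in both sets. Appendix A never computes that probability. Some of its sentences nevertheless read as joint statements, and 13.1 condenses them into one figure that supports the sample sizes.

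At stake is the stated basis for choosing 20 and 30 subjects. The reserve of 15 is also presented without any indication of how often it will be needed.

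**Working it through.** **Inputs.** Shares and minima come from Tables 1-5 in section 11.2. The condition shares add to 100.1%, so benign/atypical is taken as 62.1%. The age shares add to 99.2%, so the remaining 0.8% is kept as a category with no minimum.

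**1. The plan's own figures.** For one level with share p, P(X ≥ m) is a binomial tail. Of the 30 tenth percentiles (15 levels, two sets), 29 match exactly. The exception is Type I at n = 30, where the exact value is 2 and the plan has 1. There P(X ≤ 1) = 9.9%, so this is simulation error at a boundary. Single-level chances of meeting the minimum run from 90.6% to 100%. The one-subgroup claim is right.

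**2. Paired statements.** Within one characteristic the counts are multinomial, so no assumption about other characteristics is needed:

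P(A ≥ a and B ≥ b) = P(A ≥ a) + P(B ≥ b) − 1 + P(A < a and B < b)

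- Validation, BCC ≥ 5 and SCC ≥ 4: 0.793 + 0.762 − 1 + 0.032 = 0.587.
- Training, at least one Type I and one Type IV-VI: 1 − 0.876^20 − 0.846^20 + 0.722^20 = 1 − 0.0708 − 0.0353 + 0.0015 = 0.895.

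All ten pairs in 3.1, 3.2 and 3.5:

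| Set | Statement | Stated | Joint |
|---|---|---|---|
| Validation | SCC ≥ 4, BCC ≥ 5 | 75% | 58.7% |
| Training | SCC ≥ 2, BCC ≥ 3 | 75% | 71.2% |
| Validation | SCC ≥ 2, BCC ≥ 4 | 90% | 87.8% |
| Training | each sex ≥ 7 | 90% | 88.5% |
| Training | I ≥ 1, IV-VI ≥ 1 | 90% | 89.5% |
| Training | SCC ≥ 1, BCC ≥ 2 | 90% | 92.0% |
| Training | I ≥ 1, IV-VI ≥ 2 | 75% | 77.3% |
| Validation | I ≥ 1, IV-VI ≥ 2 | 90% | 93.9% |
| Validation | I ≥ 2, IV-VI ≥ 3 | 75% | 77.2% |
| Validation | each sex ≥ 11 | 90% | 90.1% |

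The first five fall short; the last five hold.

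**3. Section 13.1.** Representation is read as at least one subject per group.

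- Training: all three conditions 96.6%, all four Fitzpatrick groups 89.5%. Together, under independence, 0.966 × 0.895 = 0.864. Under any dependence the joint chance cannot exceed the smaller figure, 89.5%.
- Validation: 99.5% and 97.5%. Together 0.995 × 0.975 = 0.970.
- Each group taken singly exceeds 90% in both sets. The lowest is Type I in training, 1 − 0.876^20 = 92.9%.

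**4. All minima of one unselected random set.** For each characteristic, sum the multinomial probabilities over all counts at or above the minima:

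| | Condition | Fitzpatrick | Location | Age | Sex | Product |
|---|---|---|---|---|---|---|
| n = 20 | .830 | .773 | .959 | .912 | .885 | .496 |
| n = 30 | .816 | .803 | .901 | .848 | .901 | .452 |

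The product assumes independent characteristics. Under any dependence, the lower limit is 1 minus the sum of the shortfalls and the upper limit is the smallest single value: 36-77% for training and 27-80% for validation.

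**5. The route the plan uses.** A pool can supply both sets only if each level reaches the sum of its two minima. For 50 subjects the five chances are .933, .928, .978, .957 and .967, with product .783 (limits 76-93% under any dependence). The same sum gives 93% at 55, 97% at 60 and 99% at 65. As a check, drawing 500 random 40:60 schedules from each of 1,500 simulated pools gave at least one schedule meeting all minima in 79%, 93%, 97% and 99% of pools. The SMD rule is not included in any of these.

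**The case against.** Appendix A says openly that characteristics were handled one at a time, and its single-subgroup figures are correct. Half of the paired statements hold jointly, and four of the five misses are below 4 points. The one large miss is a 25th-percentile remark that sets no minimum. Section 13.1 can be read group by group, and then it is true. All of this stands, and it limits the point to specific figures.

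A reader might infer from step 4 that the study would miss its own minima about half the time. The documents do not support that. The 50% and 45% describe a single random set of fixed size, and they depend on independence between characteristics, for which the documents give no data. The plan searches 500 schedules, can add 15 subjects, and recruits with reference to Tables 1-5 (section 12.2). On the minima alone it nearly always succeeds within the cap of 65.

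What the objection does not remove: disclosing separate modelling does not make a sentence about two levels together correct, and no dependence between characteristics lifts the all-minima chance of a random set above 77% (training) or 80% (validation).

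**Conclusion.** Some stated probabilities are wrong as written, and the joint probability that matches the plan's own requirement is missing.

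- Five paired statements are too high. One is materially so (59% against 75%); the others miss by 0.5 to 3.8 points. These results need only the plan's shares.
- In 13.1 the >90% holds for each group separately and for validation (97% for conditions and skin types together). For training it does not hold jointly: about 86% under independence, at most 89.5% under any dependence.
- Fifty subjects fail to supply both sets' minima in about 1 trial in 5 (1 − 0.78 = 22% under independence; 7-24% under any dependence). The SMD rule can only add to this. The visible text does not show how the maximum SMD is formed across levels, so no figure is claimed for it.

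It would go too far to call the design unable to meet its minima, or 13.1 wrong throughout. The cap of 65 is adequate for the minima alone, and no endpoint or confidence interval is affected.

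**What to change.** In Appendix A:

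- Label the existing percentages as single-subgroup figures.
- Correct the five paired statements that miss to 59%, 71%, 88%, 88.5% and 89.5%, in the order of the table above.
- Rerun the simulation counting joint success. Report the chance that pools of 50, 55, 60 and 65 subjects yield a schedule meeting both sets' minima and the SMD limit. State the independence assumption and the limits without it.

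In 13.1:

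- Either confine the >90% to each group separately, or restate the training figure as about 86% (at most 89.5%).
- Say that the reserve is expected to be needed in about 1 trial in 5 for the minima alone.

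The cost is a rerun of an existing simulation and some revised wording. The cap of 65 is unchanged. The stated probabilities become less favourable, but the sponsor gains a usable figure for planning enrolment beyond 50.

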3.1. Underlying skin condition

There is a 90% chance (10th percentile) of seeing at least 1 SCC and 2 BCC lesions in the training set. There is a 75% chance (25th percentile) of seeing at least 2 SCC and 3 BCC lesions in the training set (Table 3.1.2).

There is a 90% chance (10th percentile) of seeing at least 2 SCC and 4 BCC lesions in the validation set. There is a 75% chance (25th percentile) of seeing at least 4 SCC and 5 BCC lesions in the validation set (Table 3.1.3).

Table 3.1.1. Underlying data by underlying skin condition.⁴

Group	% of Skin Biopsy-Receiving Population
Basal cell carcinoma (BCC)	21.2%
Squamous cell carcinoma (SCC)	16.7%
Other	62.2%

Table 3.1.2. Simulations for training set (N=20) by underlying skin condition.

Group	N sims	10 th Pctl	EV	Std Dev	Min	1 st Pctl	25 th Pctl	Median	75 th Pctl	90 th Pctl	99 th Pctl	Max
BCC	10,000	2	4.3	1.84	0	1	3	4	5	7	9	12
SCC	10,000	1	3.3	1.68	0	0	2	3	4	6	8	12
Other	10,000	10	12.4	2.17	4	7	11	12	14	15	17	20

Table 3.1.3. Simulations for validation set (N=30) by underlying skin condition.

Group	N sims	10 th Pctl	EV	Std Dev	Min	1 st Pctl	25 th Pctl	Median	75 th Pctl	90 th Pctl	99 th Pctl	Max
BCC	10,000	4	6.4	2.25	0	2	5	6	8	9	12	16
SCC	10,000	2	5.0	2.05	0	1	4	5	6	8	10	13
Other	10,000	15	18.6	2.69	9	12	17	19	20	22	25	27

3.2. Fitzpatrick Skin Type

There is a 90% chance (10th percentile) of seeing at least 1 Type I and 1 Type IV-VI lesion in the training set. There is a 75% chance (25th percentile) of seeing at least 1 Type I and 2 Type IV-VI lesions in the training set (Table 3.2.2).

There is a 90% chance (10th percentile) of seeing at least 1 Type I and 2 Type IV-VI lesions in the validation set. There is a 75% chance (25th percentile) of seeing at least 2 Type I and 3 Type IV-VI lesions in the validation set (Table 3.2.3).

Table 3.2.1. Underlying data by Fitzpatrick skin type.²²

Group	% of Population Receiving Pigmented Skin Lesion Biopsy
Type I	12.4%
Type II	34.9%
Type III	37.3%
Type IV-VI	15.4%

Table 3.2.2. Simulations for training set (N=20) by Fitzpatrick skin type.

Group	N sims	10 th Pctl	EV	Std Dev	Min	1 st Pctl	25 th Pctl	Median	75 th Pctl	90 th Pctl	99 th Pctl	Max
Type I	10,000	1	2.5	1.47	0	0	1	2	3	4	6	9
Type II	10,000	4	7.0	2.14	0	2	6	7	8	10	12	16
Type III	10,000	5	7.4	2.15	1	3	6	7	9	10	12	15
Type IV-VI	10,000	1	3.1	1.60	0	0	2	3	4	5	7	9

Table 3.2.3. Simulations for Validation Set (N=30) by Fitzpatrick skin type.

Group	N sims	10 th Pctl	EV	Std Dev	Min	1 st Pctl	25 th Pctl	Median	75 th Pctl	90 th Pctl	99 th Pctl	Max
Type I	10,000	1	3.7	1.81	0	0	2	4	5	6	8	12
Type II	10,000	7	10.5	2.59	2	5	9	10	12	14	17	21
Type III	10,000	8	11.1	2.65	2	5	9	11	13	15	18	21
Type IV-VI	10,000	2	4.7	1.98	0	1	3	5	6	7	10	14

3.3. *Lesion Anatomical Location*

The chance of seeing at least 1 limb and torso lesion in the validation set is 75%. [note: it is unlikely that we end up with only head and neck lesions but there is a material chance we will be missing at least 1 of the other locations] (Table 3.3.2).

There is a 90% chance of observing at least 1 torso lesion and a 75% chance of observing at least 1 limb lesion in the validation set. There is a 75% chance of observing at least 2 torso lesions in the validation set (Table 3.3.3).

Table 3.3.1. Underlying data by lesion anatomical location.²³

Group	% of positive BCC diagnosis population
Head and neck (head)	83%
Hands, arms, feet, or legs (limb)	7%
Torso	10%

Table 3.3.2. Simulations for training set (N=20) by lesion anatomical location.

Group	N sims	10 th Pctl	EV	Std Dev	Min	1 st Pctl	25 th Pctl	Median	75 th Pctl	90 th Pctl	99 th Pctl	Max
Head	10,000	14	16.6	1.68	10	12	16	17	18	19	20	20
Limb	10,000	0	1.4	1.13	0	0	1	1	2	3	5	8
Torso	10,000	0	2.0	1.33	0	0	1	2	3	4	6	9

Table 3.3.3. Simulations for validation set (N=30) by lesion anatomical location.

Group	N sims	10 th Pctl	EV	Std Dev	Min	1 st Pctl	25 th Pctl	Median	75 th Pctl	90 th Pctl	99 th Pctl	Max
Head	10,000	22	24.9	2.05	16	20	24	25	26	27	29	30
Limb	10,000	0	2.1	1.40	0	0	1	2	3	4	6	9
Torso	10,000	1	3.0	1.62	0	0	2	3	4	5	7	10

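### The Fitzpatrick Type I minimum for the validation set should be 2, not 1, under the plan's own 10th-percentile rule (minor)

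*Combined protocol and SAP*

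**What the plan says.** Appendix A, section 2, describes the simulation in three steps. It draws the set ("Simulate the appropriate number of subjects (20 for the training set or 30 for the validation set"), allocates categories ("Assign subgroup categories using a multinomial distribution") and counts each subgroup; "This process was repeated 10,000 times for each subject or lesion characteristic". The rule for the minimum follows: "The minimum expected number was defined as the 10th percentile". The same sentence glosses this as a 90% probability of reaching that count or more.

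For skin type, Table 3.2.1 gives Type I a share of 12.4%. Table 3.2.3 (validation set, N=30) gives Type I a 10th percentile of 1, a mean of 3.7, a standard deviation of 1.81, a 25th percentile of 2 and a 90th percentile of 6. The text of section 3.2 repeats the first of these: "There is a 90% chance (10th percentile) of seeing at least 1 Type I and 2 Type IV-VI lesions in the validation set". Table 2 in section 11.2 carries it forward as a validation range of 1 - 6.

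The lower bound is binding. The footnote to Tables 1-5 says: "Minimum value for the number of samples required in the study is the lower bound of the range (derived from 10th percentile"). Appendix C, 1.1.2, then chooses among 500 randomisation schedules: "The first schedule that simultaneously meets the minimum enrollment targets for both the Training set and Validation set", and that also has a maximum standardised mean difference (SMD) below 0.2, is the one used.

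**The concern.** The rule has an exact answer, because each category count in a multinomial draw is binomial. For Type I in the validation set, the exact answer and the printed one disagree by one subject.

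The printed value is also a criterion that the assignment procedure applies. Section 13.2.1 lists Type I as a subgroup level of its own, and section 13.2.4 plans accuracy by subgroup by adding each subgroup to the mixed model. If the validation set holds one Type I subject, that estimate cannot separate the skin type from the individual. The plan's 90% rule, applied exactly, would not allow such a set; the printed minimum does.

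**Working it through.** **Inputs.** Type I share p = 0.124 (Table 3.2.1). Validation size n = 30 (Appendix A, section 2). Multinomial assignment, so X ~ Binomial(30, 0.124). Rule: the 10th percentile, meaning the largest count reached with at least 90% probability.

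**Reproducing the rest of the row.** Mean = 30 × 0.124 = 3.72 (printed 3.7). SD = √(30 × 0.124 × 0.876) = 1.805 (printed 1.81). Exact 25th percentile = 2 and 90th percentile = 6, both as printed. The model and inputs are therefore read as the plan intends.

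**The 10th percentile.**
- P(X = 0) = 0.876^30 = 0.0188
- P(X = 1) = 30 × 0.124 × 0.876^29 = 0.0800
- P(X ≤ 1) = 0.0989, which is below 0.10
- P(X ≥ 1) = 0.9812, P(X ≥ 2) = 0.9011, P(X ≥ 3) = 0.7369

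The exact 10th percentile is 2. The printed value is 1.

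**The other limits.** Tables 1-5 hold 15 categories in two sets, so 30 lower and 30 upper limits. Against exact binomial 10th and 90th percentiles, 59 of the 60 agree. The Type I lower limit for the validation set is the only exception.

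**How a correct simulation could give 1.** With 10,000 draws the standard error of the estimated P(X ≤ 1) is √(0.0989 × 0.9011 / 10,000) = 0.0030. The 10% line lies (0.1000 − 0.0989) / 0.0030 ≈ 0.38 standard errors above the true value. The exact chance that at least 1,000 of the 10,000 draws show X ≤ 1 is 35.5%.

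**Rounding of the share.** P(X ≥ 2) equals 0.90 at p = 0.12357. A share between 12.350% and 12.357% would round to 12.4% and make 1 the exact answer. That is 0.007 of the 0.100 percentage points that round to 12.4%.

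**How often it could matter.** In an unrestricted draw of 30, exactly one Type I subject occurs 8.0% of the time. The validation set is not such a draw, because the schedule must also have an SMD below 0.2. Assume the usual two-proportion SMD for each category, |p1 − p2| / √{[p1(1 − p1) + p2(1 − p2)] / 2}:
- 1/30 in validation and 1/20 in training: SMD = 0.08, accepted
- 1/30 in validation and 2/20 in training: SMD = 0.27, rejected
- With a 39/26 split of 65 subjects: 1/39 and 1/26 give 0.07, accepted; 1/39 and 2/26 give 0.23, rejected

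So one Type I subject in validation is accepted only when the pool holds exactly two, one in each set. The chance is C(50,2) × 0.124² × 0.876^48 = 3.3% at 50 subjects, and C(65,2) × 0.124² × 0.876^63 = 0.8% at 65.

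**The case against.** The strongest defence is that the plan defines the minimum on its simulation, and a correctly programmed simulation returns 1 in about 35% of runs. On that view 1 is a legitimate output, and exact percentiles are a preference. It stands this far: there is no evidence of a coding or formula error, and the margin is thin (90.1% against 90%). It does not rescue the figure, because the rule is meant to give the count reached with 90% probability, and a binding threshold should not depend on the random seed when the exact value takes one line.

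The quoted sentence is also not false as a lower bound, since the chance of at least one Type I subject is 98.1%. It understates what the rule supports.

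It is fair to add that two subjects hardly make a Type I accuracy estimate informative, that the subgroup analysis has no target, and that the plan accepts validation minima of zero for limb lesions and for ages 20-49. All of this limits the importance of the point.

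Three stronger readings are tempting and are not supported:
- **That the 75% sentence for Type I is also wrong.** It is labelled as the 25th percentile. P(X ≥ 3) = 73.7%, so the exact 25th percentile is 2, as printed.
- **That about 8% of validation sets would be accepted with one Type I subject.** That figure ignores the SMD condition in Appendix C.
- **That the value is proven to be simulation error.** The simulation output is not in the documents, and an unrounded share just under 12.36% is unlikely but not excluded.

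**Conclusion.** The figure is wrong as written, and the point is minor. Under the plan's rule and its printed share, the exact minimum for Type I in the validation set is 2. Monte Carlo error is the most plausible cause.

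The practical effect is an occasional validation set with a single Type I subject: about 3.3% at 50 subjects and 0.8% at 65. These figures assume that the 12.4% share holds for enrolled subjects and that the SMD is a two-proportion difference computed per category. The visible part of Appendix C does not spell out the formula, so a different SMD would change them; the exact percentile of 2 does not depend on it. The choice of 30 subjects, the claim in section 13.1 of more than 90% chance of representation, and the primary endpoints are unchanged.

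**What to change.** - In Table 3.2.3, change the Type I 10th percentile from 1 to 2.
- In section 3.2 of Appendix A, change the Type I count in the 90% sentence for the validation set from 1 to 2. Leave the 75% sentence as it is.
- In Table 2, change the Type I validation range from 1 - 6 to 2 - 6.
- Carry the 2 into the Appendix C assignment targets.
- Take all percentiles from the exact binomial. Other cells lie close to the line too: for 30 subjects, P(X ≤ 11) for either sex is 10.02% and P(X ≤ 2) for SCC is 10.2%, so another run could move them.

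The cost is a few digits. The two sets together would then need at least three Type I subjects (1 training, 2 validation). On the plan's share, that has 95.6% probability among 50 subjects and 99.0% among the permitted maximum of 65, so the existing allowance of 15 extra subjects covers most of the shortfall.
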